4.6.3.4. Vital Signs and Physical Characteristics

The planned summaries are provided in the table below. The measurements analyzed for vital signs and physical characteristics include systolic BP, diastolic BP, pulse, weight, and BMI:

Analysis Type	Analysis Details						
Observed	• Includes all participants in the Safety Analysis Set who have both a baseline and at least 1						
values and	postbaseline observation.						
change by visit	• MMRM model (as described in Section 4.6) will be used.						
	See also: Table 6.2 from the Analyses and Displays for Labs white paper (PHUSE 2022)						
Summary by	• Definitions provided in Tables 31-33 from FDA's September 2022 Standard Safety Tables						
category	and Figures document will be used for the numerator.						
	○ Systolic BP (mm Hg): Level 1 (low): <90, Level 1 (high): ≥90, Level 2 (high):						
	≥120, Level 3 (high): ≥140, Level 4 (high): ≥160, Level 5 (high): ≥180						
	• Diastolic BP (mm Hg): Level 1 (low): <60, Level 1 (high): >60, Level 2 (high):						
	>90, Level 3 (high): >110, Level 4 (high): ≥120						
	• Includes participants with at least one postbaseline measurement.						
	• Statistical comparisons (using methods described in Section 4.6) will be included.						
Participants	For weight, cutoffs informed by CTCAE version 5 (Grades 1-3) will be used:						
meeting CTC	○ (Loss) decrease: Level 1: \geq 5%, Level 2: \geq 10%, Level 3: \geq 20%						
grade changes	 (Gain) increase: Level 1: ≥5%, Level 2: ≥10%, Level 3: ≥20% 						
in weight	Includes participants with both a baseline and at least 1 postbaseline observation.						
	• Statistical comparisons (using methods described in Section 4.6) will be included.						

Scatter plots (to support vital sign evaluations): Scatter plots of maximum-by-maximum measurements and minimum-by-minimum measurements will not be created a-priori. They may be created if warranted after review of the planned tables and figures, using Figures 6.3 and 6.4 from the Analysis and Displays for Labs white paper (PHUSE 2022) as the model. ADaM datasets will include variables to enable the creation of scatter plots for use in either an interactive tool or for ad-hoc figures.

4.6.3.5. Device Product Complaints

A summary and/or listing, as appropriate, of all product complaints, inclusive of device product complaints that lead to an AE and/or SAE will be included by category. Additional summaries may be provided as deemed appropriate.

4.7. Other Analyses

4.7.1. Immunogenicity

A participant is evaluable for Treatment Emergent (TE) Anti-Drug Antibody (ADA) if the participant has a non-missing baseline ADA result, and at least 1 non-missing postbaseline ADA result.

A participant who is evaluable for TE ADA is TE ADA+ if either of the following holds:

- Treatment-induced ADA: the participant has baseline status of ADA Not Present and at least 1 postbaseline status of ADA Present with titer ≥1:40, which is 2 × minimum required dilution (MRD) of the ADA assay (MRD = 1:20).
- Treatment-boosted ADA: the participant has baseline status of ADA Present and at least 1 postbaseline status of ADA Present with the titer being ≥2 dilutions (4-fold) of the baseline titer. That is, the participant has baseline (B) status of ADA Present, with titer 1:B, and at least 1 postbaseline (P) status of ADA Present, with titer 1:P and P/B≥4.

Refer to the PSAP for all definitions and additional details for immunogenicity.

All analyses will be based on all evaluable TE ADA participants. The baseline ADA status will be summarized by treatment group. The number and percentage of participants who are TE ADA+ will be summarized by treatment group. The summary will include the number and percentage of participants with treatment-induced ADA and treatment boosted ADA. A summary of titer values will be provided for participants who are TE ADA positive.

This analysis will be performed for the following periods:

- The treatment period up to treatment discontinuation, and
- The entire postbaseline period, including safety follow-up.

A number of additional analyses of the immunogenicity data from this study will be presented in an integrated summary document, alongside data from other studies. The analyses to be performed are described in the PSAP.

4.7.2. Subgroup analyses

The interaction effects will be evaluated using a significance level of 0.05, unadjusted. Subgroup analyses will be conducted as defined in this section. Additional subgroup analysis may also be performed as appropriate.

4.7.2.1. Subgroup analysis for HbA1c

The subgroups, for analyzing HbA1c and change in HbA1c from baseline to Week 26, will be defined as:

- baseline HbA1c stratum (< 8.0% and $\geq 8.0\%$);
- type of pre-study basal insulin (typical once-daily basal insulin and U-300/ NPH BID regimens);
- region (US and non-US);
- region (North America, South America, Europe, Asia);
- age (<65 years and \geq 65 years);
- gender (Female and Male);
- ethnicity (Hispanic or Latino, Not Hispanic or Latino);
- race (American Indian or Alaska Native, Asian, Black or African American, Native Hawaiian or Other Pacific Islander, and, White);
- number of Non-Insulin Antihyperglycemic Medications at baseline (≤ 1 and >1);
- estimated Glomerular Filtration Rate (eGFR) at baseline (<60, ≥ 60 to <90 and ≥ 90); and
- duration of diabetes per medical history (< median and \geq median).

A subgroup category with less than 10 participants will not be included in the analysis.

For treatment regimen estimand: Analyses for HbA1c and its change will be performed using the same ANCOVA model with the same independent variables as described in Section 4.3.2, separately for each subgroup. The missing values will be imputed by multiple imputation method same as the primary analysis for treatment regimen estimand. The statistical inference will be based on the multiple imputation framework by Rubin (1987). The p-value for treatment by subgroup interaction will be calculated using a chi-square test based on estimated treatment differences within each subgroup (see details in Appendix 13 [Section 6.13]).

For efficacy estimand: Analyses for HbA1c and its change will be performed using the same MMRM model described for the primary analysis in Section 4.3.2, separately for each subgroup. In addition, significance of all the interaction effects will be assessed using a full model including the same fixed effects given for the primary analysis model plus factors of subgroup, 2-way interaction of subgroup and treatment, 2-way interaction of subgroup and visit, and 3-way interaction of treatment, visit and the subgroup.

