## 9.3.2. Primary Endpoint/Estimand Analysis

The primary objective is to compare the HbA1c change from baseline to Week 26 between LY3209590 and insulin degludec and will be based on either of the 2 estimands: *treatment regimen estimand* for the US FDA submission and *efficacy estimand* for registrations in other countries.

The *treatment regimen estimand* will be estimated using the HbA1c data at baseline and Week 26 (Visit 22) for the EAS1, regardless of the use of study treatment or rescue medications. The missing measures at the primary endpoint will be imputed using multiple imputation by the retrieve dropout approach. The retrieved dropout participants are those who discontinue IP prior to Week 26 (Visit 22) but have non-missing measures at Week 26 (Visit 22). If there are only a limited number of retrieved participants that leads to a failure in performing the multiple imputation analysis, such as the model cannot converge, or the number of retrieved dropout participants is small, the missing HbA1c at Week 26 (Visit 22) will be imputed by return-to-baseline multiple imputations. After the imputation, the observed and imputed data will be analyzed by the analysis of covariance (ANCOVA). The model will include treatment, strata (country, and the type of basal insulin at randomization), and baseline value of the dependent variable. The statistical inference will be based on the multiple imputation framework by Rubin (1987).

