6.13. Appendix 13: Interaction Effect for Subgroup Analysis – Treatment Regimen Estimand

The ANCOVA analysis will be performed within each subgroup with multiple imputation of missing primary measures. Statistical inference over multiple imputation of missing data will be guided by Rubin (1987) to obtain $\hat{\theta}_1$ and $se(\hat{\theta}_1)$ for the treatment difference in subgroup 1, and $\hat{\theta}_2$ and $se(\hat{\theta}_2)$ in subgroup 2. Then, the distribution of treatment by subgroup interaction (difference of treatment effects) is: $\hat{\theta}_1 - \hat{\theta}_2 \sim N\left(\theta_1 - \theta_2, \left[se(\hat{\theta}_1)\right]^2 + \left[se(\hat{\theta}_2)\right]^2\right)$

A z-statistic can be contrasted such that $z = \frac{\hat{\theta}_1 - \hat{\theta}_2}{\sqrt{[se(\hat{\theta}_1)]^2 + [se(\hat{\theta}_2)]^2}} \sim N(0,1)$, under the null

hypothesis of no treatment by subgroup interaction.

For k groups (k \geq 2),

let $\hat{\boldsymbol{\theta}} = (\hat{\theta}_1, \hat{\theta}_2, ..., \hat{\theta}_k)$ and $Var(\hat{\boldsymbol{\theta}}) = diag([se(\hat{\theta}_1)]^2, [se(\hat{\theta}_2)]^2, ..., [se(\hat{\theta}_k)]^2)$. A chi-square test (with degrees of freedom = k-1) can be constructed as $T = (C\hat{\boldsymbol{\theta}})'(CVC')^{-1}(C\hat{\boldsymbol{\theta}}) \sim \chi^2_{k-1}$ where C is a matrix of contrast such that

	-1	1	0	 0	0]
C =	0	-1	1	 0	0
	0	0	0	 -1	1

7. References

- Bradley C. (ed). *Handbook of Psychology and Diabetes: A Guide to Psychological Measurement in Diabetes Research and Practice*. Chur, Switzerland: Harwood Academic Publishers; 1994. https://doi.org/10.1186/1477-7525-5-57

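### The treatment-regimen interaction test for HbA1c treats standard errors from very small categories as known, so it exceeds its 5% level if a factor has a category of about 10 to 20 participants

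*SAP*

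**What the plan says.** SAP 4.7.2.1 lists 11 factors for HbA1c at Week 26. Eight have two categories, eGFR has three, one version of region has four, and race has five. For the treatment regimen estimand the analysis is run "using the same ANCOVA model with the same independent variables as described in Section 4.3.2, separately for each subgroup". Protocol 9.3.2 gives the same covariates: "The model will include treatment, strata (country, and the type of basal insulin at randomization), and baseline value of the dependent variable". On the interaction, the section says: "The p-value for treatment by subgroup interaction will be calculated using a chi-square test based on estimated treatment differences within each subgroup".

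The only size rule is: "A subgroup category with less than 10 participants will not be included in the analysis". It counts both arms together. There is no minimum per arm and none for residual degrees of freedom.

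Appendix 13 repeats that "The ANCOVA analysis will be performed within each subgroup with multiple imputation of missing primary measures", takes an estimate and standard error from each category, and compares two categories with a standard normal z. For k categories, "A chi-square test (with degrees of freedom = k-1) can be constructed as" a quadratic form in the contrasts. No residual or Rubin degrees of freedom enter. SAP 4.7.2 sets the level: "The interaction effects will be evaluated using a significance level of 0.05, unadjusted".

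For the efficacy estimand, the same section instead tests the interaction in one full repeated-measures model.

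**The concern.** Ten participants at 2:1 are about 7 against 3. After the covariates are fitted, few degrees of freedom remain to estimate the residual variance. The standard error from such a category is noisy and often too small. A normal or chi-square reference ignores that noise, so the statistic has a heavier tail than the plan assumes.

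At stake is a false treatment-by-subgroup signal under the estimand meant for the US submission. Race is the most plausible place, because it has the most categories: 10 to 20 participants are only 10/939 = 1.1% to 20/939 = 2.1% of those randomized.

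**Working it through.** **Inputs.** SD 1.1%, 2:1 allocation, 939 randomized and 15% dropout come from SAP 5. The level of 0.05 and the minimum of 10 come from SAP 4.7.2 and 4.7.2.1. Category sizes, countries per category and the missing fraction are assumptions.

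**The plan's own figures.** Completers: 939 × 0.85 = 798. The standard error of the overall difference is 1.1 × √(1/532 + 1/266) = 0.0826. Power at a margin of 0.3% is Φ(0.3/0.0826 − 1.96) = Φ(1.67) = 95.3%, and at 0.4% it is Φ(2.88) = 99.8%. Both match SAP 5. The only figure stated for the interaction test is its 0.05 level.

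**Degrees of freedom.** The model uses an intercept, treatment, baseline, insulin type, and one term per country beyond the first. A category of 10 leaves 10 − 4 = 6 in one country, 4 across three countries and 3 across four.

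**Exact limit for one small category against a very large one.** The large category adds almost no variance, so z behaves as a t statistic. The true size is P(|t| > 1.96):

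| df | 3 | 4 | 6 | 10 | 14 | 30 |
|---|---|---|---|---|---|---|
| size | 14.5% | 12.2% | 9.8% | 7.8% | 7.0% | 5.9% |

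**Simulation with complete data.** No interaction, normal errors, one common SD, 10,000 replicates, Monte Carlo error about 0.2 to 0.35 points. With w = 1/SE² in each category and θ̄ the weighted mean, the Appendix 13 statistic equals T = Σ w(θ̂ − θ̄)². The Welch F is T/(k−1) divided by 1 + [2(k−2)/(k²−1)]·Σ(1 − w/Σw)²/df. Its denominator degrees of freedom are (k²−1)/[3Σ(1 − w/Σw)²/df].

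| Category sizes (countries in each) | Planned | Pooled F | Welch F |
|---|---|---|---|
| 10/788 (1/10) | 9.7% | 5.3% | 5.3% |
| 10/788 (3/10) | 11.5% | 4.7% | 5.1% |
| 20/778 (3/10) | 7.0% | 5.4% | 5.0% |
| 15/200/80/503 (3/5/3/8) | 7.3% | 4.9% | 5.2% |
| 20/200/100/10/468 (3/5/5/3/8) | 11.1% | 5.3% | 6.5% |
| 10/200/100/10/478 (3/5/5/3/8) | 14.1% | 5.1% | 6.9% |
| 399/399 (10/10) | 4.8% | 4.8% | 4.8% |

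With two categories, the planned test has size 9.6–13.8% when the smaller has 10, 8.4% at 15, 7.0–7.3% at 20, 6.1–6.2% at 30 and 5.4% at 50. One four-category layout with a smallest category of 20 gave only 5.9%.

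**With multiple imputation and Rubin pooling** (4,000 replicates; retrieved-dropout and return-to-baseline versions):

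| Category sizes | 3% missing | 7.5% missing |
|---|---|---|
| 10/788 | 7.8–8.5% | 6.6–7.0% |
| 20/200/100/10/468 | 8.8–9.2% | 6.0–6.3% |
| 10/200/100/10/478 | 11.6–12.2% | 8.8–9.0% |
| 399/399 | 4.2–4.8% | 3.2–3.5% |

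The Rubin variance is somewhat conservative here and offsets part of the inflation. At 10% missing (2,000 replicates), the first and third layouts gave 5.9% and 8.2%. A five-category layout with two categories of 20 gave 2.7%, below nominal.

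**Unequal residual SD across categories** (assumed ratios, 640/180/90/15/10, complete data). With SD 1.3 times larger in the two small categories, the planned test gives 12.1% and the pooled F 13.0–14.0%. At 1.5 times they give 11.5% and 19.4%. With SD about 0.77 times, the pooled F gives 2.0%.

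**The case against.** The strongest reply is that little depends on these tests. They lie outside the multiplicity scheme of SAP 2.1. Eleven independent tests at 5% would already give 1 − 0.95¹¹ = 43% chance of at least one false signal. The documents give no category counts. Categories below 10 are dropped, so material inflation needs a category in a band of roughly 10 to 30. Most factors are broad two-way splits. The planned imputation shrinks the effect, and the efficacy-estimand interaction test gives a second look at the same factors.

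Most of this stands, and it limits the point to a conditional one. It does not remove it: when a small category exists, the excess follows from the stated rule and not from chance. The efficacy-estimand test uses different data and a different model, so it does not calibrate this p-value.

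It also stands that one pooled model is not a safe remedy in general. The separate-variance test is nearly insensitive to unequal SDs; the pooled F test is not.

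A reader might infer that using different tests for the two estimands is itself a defect. It is not: the estimands differ in data, missing-data handling and model by design.

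**Conclusion.** The point holds conditionally. If a factor has a category of about 10 to 20 participants, the nominal 5% test has a true size of roughly 7% to 14% with complete data, and about 6% to 12% with imputation at 3% to 7.5% missing. At 30 participants it is about 6%, and from about 50 the excess is negligible. These figures rest on assumed category sizes, country spread and missing fractions, and on normal errors.

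Three stronger readings are not supported. A reader might infer that all the US-estimand subgroup p-values are unreliable, but factors with two large categories are unaffected. A reader might expect false treatment-by-region findings, but nothing in the documents points to a region of 10 to 20 participants; even for race, a small category is plausible and not documented. A reader might see a threat to the main results, but the tests are exploratory and unadjusted, and no primary or key secondary conclusion changes.

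**What to change.** In Appendix 13, keep the separate fits and replace the normal and chi-square references with a Welch-type t (two categories) or F (k categories) with finite degrees of freedom. Use the within-category residual degrees of freedom, or Rubin degrees of freedom adjusted so that they cannot exceed them. Unadjusted Rubin degrees of freedom, (M−1)(1 + W/[(1+1/M)B])² with M imputations and within- and between-imputation variances W and B, grow without limit as missing data vanish, so they would not cure the problem. In the complete-data layouts run, the Welch F gave about 5% to 7%.

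Because some excess remains with several tiny categories, also raise the minimum for the interaction test in 4.7.2.1, for example to about 50 with a minimum per arm, or collapse sparse categories.

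A single ANCOVA with treatment-by-subgroup terms and an F reference, in line with the efficacy estimand, is an acceptable alternative only if residual variance is similar across categories.

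The cost is SAP wording, a small program change, slightly less power, and some sparse categories shown descriptively only.

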4.7.2.2. Subgroup analysis for Participant-Reported Hypoglycemic Events

The subgroups, for analyzing documented Level 2/3 hypoglycemia, non-nocturnal and nocturnal hypoglycemia rates during 0-78 weeks, will be defined as:

• baseline HbA1c stratum (< 8.0% and $\ge 8.0\%$);

- type of pre-study basal insulin (typical once-daily basal insulin and U-300/NPH BID regimens);
- age (<65 years and \geq 65 years);
- region (US and non-US);
- region (North America, South America, Europe, Asia); and
- estimated glomerular filtration rate (eGFR) at baseline (<60, \geq 60 to <90 and \geq 90 mL/min/1.73 m²).

The hypoglycemia rates will be analyzed using a negative binomial regression including the same independent variables for hypoglycemia event analyses (see Section 4.6.3.1), separately for each subgroup. The interaction effects will be evaluated using a full model using a negative binomial regression including the same independent variables plus factors of subgroup, 2-way interaction of subgroup and treatment.

4.8. Interim Analyses

4.8.1. Data Monitoring Committee (DMC)

An independent external DMC will be responsible for reviewing unblinded data during the study. The committee will include 4 clinicians and 1 statistician who are independent experts not involved in the study. The DMC will review unblinded safety data to ensure the safety of study participants and some efficacy data to confirm a reasonable risk-benefit profile. A subset of analyses described above in Sections 4.3 to 4.6 will be provided for the DMC review. The external Statistical Analysis Center statistician/analyst will generate the unblinded reports and confidentially distribute the unblinded reports to DMC members. Study team will remain blinded to study treatment until the planned unblinding occurs. The DMC will be conducted to maintain study integrity. Details of DMC is included in the DMC charter.

4.9. Changes to Protocol-Planned Analyses

There are no changes to the analyses described in the protocol but additional details are provided.

5. Sample Size Determination

Approximately 939 participants will be randomly assigned to LY3209590 and insulin degludec in a 2:1 ratio. With the assumption of 15% dropout at Week 26 (Visit 22), approximately 532 and 266 participants will complete 26 weeks of treatment on LY3209590 and insulin degludec, respectively.

The primary objective of this study is to test the hypothesis that LY3209590 is noninferior to insulin degludec on glycemic control as measured by change from baseline to Week 26 (Visit 22) in HbA1c in participants with T2D currently on basal insulin.

Assuming a NIM of 0.4%, no true difference between treatment groups, and a SD of 1.1%, 798 completers (532 on LY3209590 and 266 on insulin degludec) will provide greater than 99% statistical power to show noninferiority between LY3209590 and insulin degludec using the upper limit of a 2-sided 95% confidence interval (LY3209590 – insulin degludec). This sample size also has at least 95% statistical power to show noninferiority between LY3209590 and insulin degludec) and insulin degludec using a 0.3% NIM at Week 26 (Visit 22).

The 798 completers will provide 95% statistical power to demonstrate the superiority (LY3209590 vs. insulin degludec) of change in HbA1c from baseline to 26 weeks (assuming a SD of 1.1% and true mean difference is -0.3%) using the alpha of 0.05.

The 798 completers will provide at least 95% statistical power to show the superiority of the percentage of time in glucose range between 70 and 180 mg/dL (3.9 and 10.0 mmol/L) inclusive during the CGM session prior to Week 26 (Visit 22) between LY3209590 and insulin degludec (assuming a SD of 18% and true mean difference is 5%) at alpha = 0.05.

The 798 participants will provide at least 80% statistical power to show the superiority of the event rate of clinically significant nocturnal hypoglycemia (<54 mg/dL [3.0 mmol/L] or severe) during treatment phase up to Week 78 (assuming event rate of 0.67 [SD = 2.6] and 1.1 [SD = 2.6] events per participant per year for LY3209590 and insulin degludec, respectively) using a negative binomial distribution at alpha = 0.05.

6. Supporting Documentation

6.1. Appendix 1: Demographic and Baseline Characteristics

Demographic and baseline characteristics including but not limited to age (years), age groups (<65, \geq 65 and <75, \geq 75 and <85, \geq 85 years), sex, ethnicity, race, country, region, height, weight (kg), body mass index (BMI: kg/m²), BMI groups (<25, \geq 25 and <30, \geq 30 and <35, \geq 35 kg/m²), eGFR groups (<30, \geq 30 and <60, \geq 60 and <90, \geq 90 mL/min/1.73 m²), duration of diabetes (years), HbA1c at screening, HbA1c stratum at screening (<8.0% and \geq 8.0%), baseline HbA1c, baseline HbA1c stratum (<8.0% and \geq 8.0%), fasting serum glucose (mmol/L and mg/dL), type of pre-study basal insulin, baseline non-insulin antihyperglycemic medications (type and number) will be summarized by treatment group using the mITT, Randomized Population (if different from the mITT) and mITT Population, excluding inadvertently enrolled participants.

Continuous measures will be summarized using descriptive statistics and treatment difference will be analyzed using the analysis of variance. Categorical measures will be summarized using sample size, frequency, and percentage and treatment difference will be analyzed using Chi-squared test.

The by-participant listing of demographic and baseline characteristics will be provided for Randomized Population.

Historical conditions are conditions that end prior to inform consent and preexisting conditions are conditions that are still ongoing at inform consent. The number and percentage of participants with historical conditions will be summarized by treatment group using MedDRA PT using the mITT, Randomized Population (if different from the mITT) and mITT Population, excluding inadvertently enrolled participants. Events will be ordered by decreasing frequency. Similar summary will also be provided for preexisting conditions.

